6.0 STUDY DESIGN AND DESCRIPTION

6.1 Study Design

AR14.001 is a global phase 3, efficacy and safety study of AZM in children aged 6 to <18 years with primary or secondary hypertension. At least 213 subjects will participate in a 6-week, double-blind, randomized, treatment phase (DB Phase), followed by a 2-week, double-blind, randomized placebo-controlled withdrawal (Withdrawal Phase). In the DB Phase, subjects will be randomized (1:1:1:1) with AZM (high, intermediate, or low) using 4 doses (10, 20, 40, and 80 mg) or losartan. In the Withdrawal Phase, subjects will be randomized (1:1) to continue taking their previously assigned active treatment or to be switched to placebo. This study also includes a 44-week, OL extension (OL Phase) in which all subjects will receive AZM and other antihypertensive medications (if needed) according to a titrate-to-target BP algorithm. The study will be conducted at approximately 120 sites. BP will be assessed in the clinic throughout the study, and subjects may also participate in a 24-hour ABPM procedure at Baseline, at the end the DB Phase and at the end of the OL Phase.

A schematic of the study design is included as [Figure 6.a](#). A schedule of study procedures is listed in [Section 9.b](#).

Figure 6.a Schematic of Study Design

AZM-L=low-dose AZM, AZM-M=intermediate-dose AZM, AZM-H=high-dose AZM, RZ=Randomization, D=Day, W=Week.

(a) β -blocker use should be tapered off gradually during the first week of the washout. If seDBP remains below inclusion criterion #4 (Section 7.1) after the washout, it can be extended in 1-week increments up to 2 times, for a maximum washout of 4 weeks (for currently treated subjects only). Placebo should continue during the extension(s).

(b) All subjects randomized to AZM-M, AZM-H or losartan will be force-titrated at Week 2.

(c) If possible, the procedures planned for Week 8 or 52 should be completed at the time of discontinuation for subjects who prematurely withdraw from double-blind or OL treatment, respectively.

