13.1.2 Analysis of Demographics and Other Baseline Characteristics

Demographic and baseline characteristics (eg, age, race, gender, height, weight, kidney function, and hypertension diagnosis) will be summarized using descriptive statistics for each study phase by treatment group and overall (eg, mean, SD, median, minimum and maximum values, and the number and percentage of subjects in specified categories). Unless otherwise specified, baseline

values used to summarize all 3 phases (DB, withdrawal and open-label) will be the last obtained value prior to treatment in the DB phase.

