For the 44-week, OL extension phase descriptive statistics will be presented on subjects overall (ie, all subjects) and by status of additional antihypertensive use for the endpoints collected during the extension phase as follows: (a) Change from Baseline at each study visit and at the Final/End-of-Study Visit in trough clinic seSBP, seDBP, and MAP and (b) The number and percent of subjects achieving target BP at the end of the 44-week open-label extension period. Baseline for the OL Phase will be the last value prior to the first dose of study drug in the DB Phase.

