3.6. Changes to Analysis from Protocol

Refer to Section 3.5.

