6.1. REFERENCE START DATE AND STUDY DAY

Reference start date is defined as the day of the first dose of study medication, (Day 1 is the day of the first dose of study medication) and will appear in every listing where an assessment date or event date appears.

Study Day will be calculated from the reference start date and will be used to show start/ stop day of assessments and events.

Study day will be calculated as follows:

- If the date of the event is on or after the reference date, then:
 - Study Day = (date of event reference date) + 1.
- If the date of the event is prior to the reference date, then:
 - Study Day = (date of event reference date).

In the situation where the event date is partial or missing, Study Day, and any corresponding durations will appear partial or missing in the listings.

6.2. **BASELINE**

Unless otherwise specified, baseline is defined as the last non-missing measurement taken prior to reference start date (including unscheduled assessments). In case where the last non-missing measurement and the reference start date coincide, that measurement will be considered pre-treatment.

2014-000674-18 Statistical Analysis Plan Version 7.0 7.0 Document: Version Number: Author: Version Date: 13JAN2020

Template No.: CS_TP_BS016 Revision 5 Reference: CS_WI_BS005

Effective Date: 01Apr2018

7.0

13JAN2020

Version Date:

For subjects randomized but not treated, baseline is defined as the last non-missing measurement taken on or before randomization.

Document: 2014-000674-18 Statistical Analysis Plan Version 7.0 Version Number:

Township No. 00 TD D0046 Davision 5

Template No.: CS_TP_BS016 Revision 5 Reference: CS_WI_BS005

Effective Date: 01Apr2018

Author:

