15.3.3. Analysis of Additional Efficacy Variables

15.3.3.1.

Change from baseline in trough clinic seDBP, seSBP, and MAP at visits Week 2 and Week 4 of DB Phase will be will be analyzed using the same MMRM model that is described in section 15.2.3.2 and the result will come from the same model as well.

15.3.3.2.

No statistical model will be used for Change from Baseline in trough clinic seDBP, seSBP, and MAP at all visits of the OL Phase, including Week 52/Final Visit. Only descriptive statistics will be provided

15.3.3.3.

The analysis for whether a subject who achieves the BP targets at Week 6/Final Visit in the DB Phase (for seSBP, seDBP, both), will be logistic models on observed data with treatment (AZM low, med, high dose and losartan), age (Tanner stage <3, ≥3), race (Black or African American, Non- Black or African American) and weight (<50 kg, ≥50 kg) as fixed effects and baseline clinic seated BP as a covariate. The number and percentage of subjects who achieved target BP will be presented, along with the odds ratios and associated 95% CIs. Sensitivity analyses on trough seDBP, seSBP, and both will be performed for DB analysis on observed values and using multiple imputation for missing trough BP data to assess the impact of LOCF methodology and drop-outs. For Week 52/Final Visit of the OL Phase, the number and percentage of subjects who achieve the BP targets will be provided.

For subjects with CKD, the analysis for weather a subject who achieves the BP targets at week 6/Final Visit in the DB phase and week 8/Final visit in the WD phase (for seSBP, seDBP, both), will be logistic models on observed data with treatment (AZM low, med, high dose and losartan), age (Tanner stage <3, ≥3), race (Black or African American, Non- Black or African American) and weight (<50 kg, ≥50 kg) as fixed effects and baseline clinic seated BP as a covariate. The number and percentage of subjects who achieved target BP will be presented, along with the odds ratios and associated 95% Cls. . Sensitivity analyses on trough seDBP, seSBP, and both will be performed for DB analysis on observed values and using multiple imputation for missing trough BP data to assess the impact of LOCF methodology and drop-outs. For Week 52/Final Visit of the OL Phase, the number and percentage of subjects with CKD who achieve the BP targets will be provided.

7.0 Document: 2014-000674-18 Statistical Analysis Plan Version 7.0 Version Number: Author: Version Date: 13JAN2020

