16. SAFETY OUTCOMES

All outputs for safety outcomes will be based on the Safety Analysis Set.

There will be no statistical comparisons between the treatment groups for safety data, unless otherwise specified with the relevant section.

Safety analyses will be presented separately for the different study phases (i.e., DB, Withdrawal, and OL Phases). Summaries for the DB and Withdrawal Phases will be by Overall (i.e., all subjects), AZM treated subjects (pooled), and by the individual treatments; summaries for the OL Phase will by Overall and by status of additional antihypertensive use (i.e., AZM alone and AZM plus additional antihypertensive).

For safety analysis, baseline value for the DB Phase analyses will be the last available value prior to the first dose of DB Phase study drug. Baseline value for the Withdrawal Phase will be the last available value from the DB Phase. Baseline value for the OL Phase will be the last available value prior to the first dose of DB Phase study drug.

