All the data collected for procedures (Con Meds, Vital Signs, AE assessments, Laboratory tests, Pregnancy tests) at Visit 8/ W6 will be used as visit 8/W6/last visit of DB phase in DB analysis and as WD phase baseline in WD phase analysis because all the measurements are taken before WD phase drug is given to the subjects at Visit 8/W6.

All the data collected for procedure (Con Meds, Vital Signs, Physical Examination, AE assessments, Laboratory tests, Pregnancy tests, ECG) at Visit9/ W8 will be used as visit 9/W8/last visit of WD Phase in WD phase analysis and OL baseline in OL analysis because all the measurements are taken before OL drug is given to the subjects at Visit 9/ W8.

Visit 4/Day 1 - First day of Double-Blind Dose Visit 8/Week 6 - First day of Withdrawal Phase Dose Visit 9/Week 8 – First day of Open Label Dose

LISTINGS

All listings will be ordered by the following (unless otherwise indicated in the template):

- Site-subject ID,
- Randomized treatment group (or treatment received if it's a safety output), first by active dose [by ascending dose group] and then control/placebo
- Phase
- Visit
- Date (where applicable),
- For listings where non-randomized subjects are included, these will appear in a category after the randomized treatment groups labelled 'Not Randomized'.

GENERAL DISPLAY

When a table/listing is split in multiple pages, the footnotes added to explain the table/listing should be displayed on each page of the table/listing and not only on the last one.

Document: 2014-000674-18 Statistical Analysis Plan Version 7.0

Version Number:

Version Date: 13JAN2020

7.0

Template No.: CS_TP_BS016 Revision 5 Reference: CS_WI_BS005

Effective Date: 01Apr2018

Author:

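### SAP Appendix 1 makes Week 8 the open-label baseline, while SAP 16 and protocol 13.1.3 and 13.1.5 use the last value before double-blind dosing

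*SAP*

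**What the plan says.** SAP Appendix 1, under the definition of phases and treatment assignment, lists the procedures done at Visit 9/Week 8 (among them vital signs, laboratory tests and ECG). It says these data "will be used as visit 9/W8/last visit of WD Phase in WD phase analysis and OL baseline in OL analysis". The reason given is that they are collected before the first open-label dose.

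The other baseline statements differ:

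- SAP 16, for safety: "Baseline value for the OL Phase will be the last available value prior to the first dose of DB Phase study drug". Protocol 13.1.5 has the same rule.
- Protocol 13.1.3, directly after listing the open-label summaries of seSBP, seDBP and MAP: "Baseline for the OL Phase will be the last value prior to the first dose of study drug in the DB Phase".
- Protocol 13.1.2, for baseline characteristics: "values used to summarize all 3 phases (DB, withdrawal and open-label) will be the last obtained value prior to treatment in the DB phase".
- SAP 6.2, the general default: "Unless otherwise specified, baseline is defined as the last non-missing measurement taken prior to reference start date", where the reference start date is the first dose of study medication on Day 1.

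SAP 3.6, on changes from the protocol, reads only "Refer to Section 3.5", which is the sample-size section.

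**The concern.** The same open-label tables have two incompatible baselines in current text, and the SAP gives no order of precedence. Protocol 6.1 explains why the choice matters: after six weeks of active treatment, "subjects will be randomized (1:1) to continue taking their previously assigned active treatment or to be switched to placebo" for Weeks 6 to 8. A Week 8 reference is therefore on-drug for about half the subjects and two weeks off drug for the rest. Open-label summaries are presented overall and by add-on antihypertensive use, not by withdrawal assignment, so a reader could not see the mixture.

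If Appendix 1 is programmed, these outputs change:

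- change from baseline in clinic seDBP, seSBP and MAP at every open-label visit (SAP 15.3), and the vital-sign changes (SAP 16.4);
- laboratory change from baseline and shift tables (SAP 16.2);
- the markedly-abnormal flags defined relative to baseline (SAP Appendix 3): creatinine, haemoglobin, haematocrit and RBC count.

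These outputs serve the secondary objective of long-term open-label safety and tolerability. Timing adds to the problem. Double-blind and withdrawal data are unblinded and analysed once all subjects pass Week 8 (SAP 4.2), before the open-label analysis (SAP 4.3). An unresolved conflict leaves the reference open to choice after Week 8 results by arm are known.

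**Working it through.** The plan states no figure to reproduce. The check is a comparison of the texts, followed by an illustration of size.

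**Is the Appendix 1 clause operative?**

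1. Appendix 1 has a parallel sentence making Visit 8/Week 6 data the withdrawal-phase baseline. SAP 16 also takes the withdrawal baseline from the last double-blind value. The Week 6 sentence thus works as a real baseline rule, and the Week 8 sentence has the same form.
2. SAP 6.2 does not settle the matter, because it yields wherever something else is specified, and Appendix 1 specifies something else.
3. For safety, the SAP contradicts itself (Section 16 against Appendix 1). For open-label efficacy, the SAP body has only the 6.2 default, so the explicit conflict is with protocol 13.1.3.

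**Week 8 mix by design.** With 1:1:1:1 and then 1:1 allocation:

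- placebo 0.50
- AZM 0.75 × 0.5 = 0.375
- losartan 0.25 × 0.5 = 0.125

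**Size for seDBP.** Inputs:

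- the 4.5 mmHg design difference (protocol 13.3), assumed to hold at Week 8 among subjects entering the open-label phase;
- A, the mean Day 1 to Week 8 fall in subjects kept on AZM, which the documents do not give.

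The reported reduction shrinks by the mean Day 1 to Week 8 fall.

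- AZM-arm subjects: 0.5 × A + 0.5 × (A − 4.5) = A − 2.25.
- If placebo subjects are on average no higher than on Day 1, then A − 4.5 ≥ 0, so A ≥ 4.5 and the understatement is at least 2.25 mmHg. Each further 1 mmHg of A adds 1 mmHg.
- For an assumed difference d in place of 4.5, this floor is d/2: 1.5 mmHg at d = 3 and 3.0 mmHg at d = 6.
- All subjects, with an assumed losartan–placebo difference dL and the same condition: 0.75 × 2.25 + 0.25 × dL/2 = 1.6875 + 0.125 × dL. This is 1.69 mmHg at dL = 0 and 2.25 mmHg at dL = 4.5.
- Two AZM-arm groups with equal Day 1 and equal open-label values would differ by 4.5 mmHg in reported change solely through withdrawal assignment.

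**Laboratory flags.** Appendix 3 lists 5 haematology + 14 chemistry + 9 urinalysis = 28 distinct tests, of which 4 are relative to baseline. The creatinine flag is more than 1.5 times baseline. If Week 8 creatinine is a fraction r above Day 1 (assumed), the flag needs 1.5 × (1 + r) times Day 1:

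| r | Threshold relative to Day 1 |
|---|---|
| 0 | 1.50 |
| 0.10 | 1.65 |
| 0.20 | 1.80 |

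The direction for the three haematology flags is not known.

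**The case against.** The strongest reply is that this is a drafting slip that would do no harm. The clause sits in an appendix of output conventions, and its list includes items with no change from baseline, such as concomitant medications and pregnancy tests. It could be a rule for assigning boundary visits to phases. A programmer would have to set aside SAP 16 to get the laboratory tables wrong, and protocol 13.1.3 is explicit for blood pressure. The table templates mentioned in SAP 8 are not among the documents and may fix the baseline.

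Part of this stands. The consequences arise only if Appendix 1 is followed, and the templates might prevent that. It does not remove the contradiction: the sentence names a baseline, gives a reason for it, and matches an operative rule for Week 6.

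The limits on size also stand:

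- The 4.5 mmHg is the difference the trial is powered to detect, not a forecast. The direction of the blood pressure effect depends on A exceeding 2.25 mmHg.
- Subjects withdrawn for confirmed high blood pressure on blinded treatment do not enter the open-label phase, so the full randomised contrast may not carry over.
- The statement in protocol 4.1.5 that creatinine rises reversed off drug concerns adults, most of whom were also taking diuretics. It shows that a raised reference is possible, mainly in subjects kept on active drug, but not that flags will be missed.
- Protocol 13.1.2 is weak support, since it covers baseline characteristics and allows exceptions. The case rests on protocol 13.1.3 and 13.1.5 and SAP 16.

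Open-label blood pressure change is descriptive: "No statistical model will be used for Change from Baseline in trough clinic seDBP, seSBP, and MAP at all visits of the OL Phase".

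**Conclusion.** The concern holds. Appendix 1 contradicts SAP 16 and the protocol, and the SAP declares no change. This should be corrected before open-label programming. Confidence in the contradiction is high. The mmHg and creatinine figures are illustrations under the stated assumptions, and the true shift cannot be derived from the documents.

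The reach is limited. No hypothesis test, type I error or power is involved. Open-label target-BP attainment, ABPM change (there is no Week 8 recording) and laboratory flags based on fixed or reference-range limits do not depend on this baseline.

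**What to change.** In SAP Appendix 1, delete the words that make Week 8 data the open-label baseline and keep the rest of the sentence, which assigns them to the end of the withdrawal phase. State once, for efficacy and safety together, that open-label change is measured from the last value before the first double-blind dose. Check the table templates against that statement. If change from Week 8 is also wanted, define it as a separate, labelled supplementary summary and record it in SAP 3.6. The cost is one SAP sentence, with no new data.

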APPENDIX 2. Partial Date Conventions

Imputed dates will NOT be presented in the listings.

ALGORITHM FOR TREATMENT EMERGENCE OF ADVERSE EVENTS:

START DATE	STOP DATE	ACTION
Known	Known	If start date < study med start date, then not TEAE If start date >= study med start date, then TEAE
	Partial	If start date < study med start date, then not TEAE If start date >= study med start date, then TEAE
	Missing	If start date < study med start date, then not TEAE If start date >= study med start date, then TEAE
Partial, but known components show that it cannot be on or after study med start date	Known	Not TEAE
	Partial	Not TEAE
	Missing	Not TEAE
	J	
Partial, could be on or after study med start date	Known	If stop date < study med start date, then not TEAE If stop date >= study med start date, then TEAE
	Partial	If Informed consent year and AE start year is same and study med start year is later, impute start date to informed consent date. If study med start year and AE start year is same, impute start date to study med start date If study med start year is earlier then 2016, impute the start date to first day of the year Impute stop date as latest possible date (i.e. last day of month if day unknown or 31st December if day and month are unknown), then: If stop date < study med start date, then not TEAE If stop date >= study med start date, then TEAE
	Missing	Assumed TEAE
Missing	Known	If stop date < study med start date, then not TEAE If stop date >= study med start date, then TEAE

Document: 2014-000674-18 Statistical Analysis Plan Version 7.0

Version Number:

Version Date:

7.0 13JAN2020

Template No.: CS_TP_BS016 Revision 5

Reference: CS_WI_BS005

Effective Date: 01Apr2018

Author:

START DATE	STOP	ACTION
	DATE	
	Partial	Impute stop date as latest possible date (i.e. last day of
		month if day unknown or 31st December if day and
		month are unknown), then:
		If stop date < study med start date, then not TEAE
		If stop date >= study med start date, then TEAE
	Missing	Assumed TEAE

ALGORITHM FOR MEDICATION HISTORY / CONCOMITANT MEDICATIONS:

START DATE	STOP DATE	ACTION
Known	Known	If Informed consent date > medication end date ≥ Informed consent date -30, assign as Medication History
		If start date >= study med start date, assign as concomitant
	Partial	Impute stop date as latest possible date (i.e. last day of month if day unknown or 31st December if day and month are unknown), then:
		If Informed consent date > medication end date ≥ Informed consent date -30, assign as medication history
		If stop date >= study med start date and start date <= end of treatment, assign as concomitant
		If stop date >= study med start date and start date > end of treatment, assign as post treatment
	Missing	If stop date is missing could never be assumed a prior medication
		If start date <= end of treatment, assign as concomitant
		If start date > end of treatment, assign as post treatment
Partial	Known	Impute start date as earliest possible date (i.e. first day of month if day unknown or 1 st January if day and month are unknown), then:
		If Informed consent date > medication end date ≥ Informed consent date -30, assign as medication history
		If stop date >= study med start date and start date <= end of treatment, assign as concomitant
		If stop date >= study med start date and start date > end of treatment, assign as post treatment

Document: 2014-000674-18 Statistical Analysis Plan Version 7.0 Version Number: 7.0

Author: Version Date: 13JAN2020

Template No.: CS_TP_BS016 Revision 5 Reference: CS_WI_BS005

Effective Date: 01Apr2018

7.0

START DATE	STOP DATE	ACTION
	Partial	Impute start date as earliest possible date (i.e. first day of month if day unknown or 1 st January if day and month are unknown) and impute stop date as latest possible date (i.e. last day of month if day unknown or 31 st December if day and month are unknown), then: If Informed consent date > medication end date ≥ Informed consent date -30, assign as prior If stop date >= study med start date and start date <= end of treatment, assign as concomitant If stop date >= study med start date and start date > end of treatment, assign as post treatment
	Missing	Impute start date as earliest possible date (i.e. first day of month if day unknown or 1st January if day and month are unknown), then: If stop date is missing could never be assumed a medication history If start date <= end of treatment, assign as concomitant If start date > end of treatment, assign as post treatment
Missing	Known	If Informed consent date > medication end date ≥ Informed consent date -30, assign as medication history If stop date >= study med start date, assign as concomitant Cannot be assigned as 'post treatment'
	Partial	Impute stop date as latest possible date (i.e. last day of month if day unknown or 31 st December if day and month are unknown), then: If Informed consent date > medication end date ≥ Informed consent date -30, assign as medication history If stop date >= study med start date, assign as concomitant Cannot be assigned as 'post treatment'
	Missing	Assign as concomitant

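### When both adverse-event dates are partial, SAP Appendix 2 resets a same-year start to the first dose even if a later month is recorded, so a later-phase event can be counted under the double-blind arm

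*SAP*

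**What the plan says.** SAP Appendix 2 decides treatment emergence from a table of start-date and stop-date completeness. The row at issue is headed "Partial, could be on or after study med start date". Its three stop-date cells work differently:

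- **Known stop:** the stop date alone decides, and no start is imputed.
- **Missing stop:** the event is taken as treatment-emergent, and no start is imputed.
- **Partial stop:** the start is imputed by three rules. The first concerns events in the consent year when dosing began in a later year. The second is "If study med start year and AE start year is same, impute start date to study med start date". The third is "If study med start year is earlier then 2016, impute the start date to first day of the year". The stop date is then completed ("Impute stop date as latest possible date (i.e. last day of month if day unknown or 31st December if day and month are unknown), then") and compared with first dose to decide treatment emergence.

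Elsewhere in this table, known components of a start date serve only to rule an event out, in the row "Partial, but known components show that it cannot be on or after study med start date".

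The medication table in the same appendix keeps a known month: "Impute start date as earliest possible date (i.e. first day of month if day unknown".

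SAP 16.1 defines treatment-emergent events within each phase by onset date and refers to Appendix 2 for partial dates. SAP 6.1 says "Reference start date is defined as the day of the first dose of study medication" and calls that day Day 1. Appendix 1 says "Visit 4/Day 1 - First day of Double-Blind Dose".

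**The concern.** A recorded month is real information about when an event began. The same-year rule discards it and substitutes the earliest date on treatment. If that date also fixes the phase, an event known to have begun months into open-label treatment is reported in the Double-Blind Phase, under whichever arm the subject was first randomised to.

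All subjects take AZM in the Open-Label Phase (SAP 3.3; Protocol 6.1.5). An open-label AZM event in a subject randomised to losartan would then appear in the losartan column. An event on placebo in the Withdrawal Phase could likewise move to an active double-blind arm. Safety of AZM relative to placebo and losartan is a secondary objective (Protocol 5.1.2; SAP 2.2), so the treatment column matters.

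The third rule depends on a fixed calendar year, for which the SAP gives no reason, and it also ignores the month.

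**Working it through.** The plan gives no figure on this point, so there is nothing to reproduce. The check applies the text to dates.

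**Inputs.** Phase limits are from SAP Appendix 1: Day 1, Week 6 (+42 days), Week 8 (+56) and Week 52 (+364). Illustrative assumptions: first dose 10 February of a 365-day year; start recorded as September of that year, day unknown; stop recorded as October, day unknown.

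**Example.**
1. September is after 10 February, so the event is in the row for starts possibly on or after first dose. The stop is partial, so the imputation cell applies.
2. The years match, so the start becomes 10 February, which is Day 1.
3. Week 6 = 10 Feb + 42 = 24 March. Week 8 = 10 Feb + 56 = 7 April. Week 52 = 10 Feb + 364 = 9 February of the next year. Every day of September is in the Open-Label Phase.
4. From 10 February to 1 September: 18 + 31 + 30 + 31 + 30 + 31 + 31 + 1 = 203 days; 203/7 = 29 weeks. If the true day was 30 September, the shift is 203 + 29 = 232 days.
5. Treatment emergence: the stop becomes 31 October, which is after first dose, so the event is treatment-emergent whatever start is imputed.
6. Keeping the month: the later of 10 February and 1 September is 1 September, which is in the Open-Label Phase.

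**Reach of the rule.** Assume first dose is uniform over a 365-day year and onset is uniform over the 309 open-label days (offsets 56 to 364). With first dose k days after 1 January, 309 − k of those days fall in the same year (none once k reaches 309).
- Average share: (309 × 310/2)/(365 × 309) = 47,895/112,785 = about 42%.
- By first-dose date: 1 January 309/309 = 100%; 1 April 219/309 = 71%; 1 July 128/309 = 41%; 1 October 36/309 = 12%; after 5 November, none.
- For about 91% of the same-year days, the month alone proves open-label onset. The current rule places none of them in open label. The month-keeping rule places that 91% there and leaves about 9% earlier (about 3% in the Double-Blind Phase).
- For Withdrawal Phase days, about 87% share the first-dose year.

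These are shares of days, not counts of events.

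**The 2016 clause, by case (start and stop both partial).**

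| First dose | AE start year | What the cell gives |
|---|---|---|
| Before 2016 | Same year | Two rules apply: first-dose date, or 1 January. No precedence stated |
| Before 2016 | Following year | 1 January, whatever month is recorded |
| 2016 or later | Same year | First-dose date, whatever month is recorded |
| 2016 or later | Following year | No start rule |

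Under the same assumptions about 58% of open-label days (100 − 42) fall in the following year. The last row is probably not empty: Protocol Amendment 01, dated 12 December 2018 (SAP 3.2), was still revising the expected enrolment mix.

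**The case against.** The strongest reply is that the table exists to decide treatment emergence, and in this cell the stop date alone does that. No sentence says that the imputed start also selects the phase. That is an inference from the SAP 16.1 cross-reference. It stands as a caveat, but the imputed start has no other evident purpose in the cell.

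Where the event lands is also open to argument. Appendix 2 does not define the study medication start date. SAP 6.1 and Appendix 1 point to the first double-blind dose, whereas Protocol 10.2.1.1 treats the Day -14 run-in dose as the first study medication. SAP 16.1 uses on-or-after in its general definition but only after in the double-blind window, so a strict reader could put a Day 1 onset outside that window. These points justify saying that the event can be counted in the Double-Blind Phase, not that it must be. Neither alternative returns it to the Open-Label Phase.

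It can also be said that recorded dates remain visible, because Appendix 1 lists them with dashes for missing parts. That is so, but Appendix 2 keeps imputed dates out of the listings, so the shift would show only by cross-checking tables against listings.

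The consent-year rule ignores a known month too. It needs the event's year to precede the first-dose year, and the row for starts that cannot be on or after first dose already covers that, so it adds nothing here.

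A reader might infer that every partially dated event is misplaced. The documents do not support this. The reset needs a partial stop as well. A start recorded in the first-dose month is placed defensibly, and a year-only start cannot be shown to be wrong. Events with a known or missing stop get no imputed start at all, which is a separate gap.

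**Conclusion.** The point holds as a minor one. When start and stop are both partial and the years match, the rule overrides a recorded later month, and an event known to belong to the Withdrawal or Open-Label Phase can be tabulated in the Double-Blind Phase under the randomised arm. In the example the displacement is at least 203 days. The conclusion rests on two readings: that the imputed start drives phase assignment, and that the study medication start date is the first double-blind dose.

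The number of affected events cannot be computed, because the documents do not say how many events have both dates partial. It is probably small. Whether an event is treatment-emergent does not change, and efficacy analyses are not touched.

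A reader might go further and infer a biased comparison of AZM with losartan. The documents do not support that: the rule applies to all arms alike, no direction of bias is shown, and SAP 16 plans no statistical comparison of safety data unless otherwise specified.

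**What to change.** In the cell where both dates are partial, replace the same-year and 2016 rules with:

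- **Month known:** impute the later of the first double-blind dose date and the first day of the recorded month. This keeps a known month, as the medication table already does.
- **Only the year known:** impute the later of 1 January of that year and the first double-blind dose date.
- State that phase and treatment column are assigned from the imputed date.

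Deleting the 2016 clause removes the overlap for early first doses, and the new rules cover starts in the year after first dose.

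The cost is a few lines of SAP text and code. Two limits remain. An event whose month straddles a phase boundary will still fall in the earlier phase (about 9% of same-year open-label days under the uniform assumptions). A year-only start in the first-dose year still goes to first dose, as now.
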